6.6.2. Hypoglycemic Episode

According to the International Consensus Statement (Battelino et al, 2023), the CGM-determined hypoglycemic episodes for Level 1 or 2 and Level 2 are defined as below:

Hypoglycemia Level	Starting Time	Ending Time	Duration
Level 1 or 2 hypoglycemia (BG <70 mg/dL [3.9 mmol/L])	Time of the 1st BG of BGs <70 mg/dL for ≥15 consecutive minutes	Time of the last BG of the BGs ≥70 mg/dL for ≥15 consecutive minutes	Time of the last BG <70 mg/dL – time of the 1st BG <70 mg/dL
Level 2 hypoglycemia (BG <54 mg/dL [3.0 mmol/L])	Time of the 1st BG of BGs <54 mg/dL for ≥15 consecutive minutes	Time of the last BG of the BGs ≥54 mg/dL for ≥15 consecutive minutes	Time of the last BG <54 mg/dL – time of the 1st BG <54 mg/dL
Level 2 hypoglycemia ending with BG ≥70 mg/dL (start with BG <54 g/dL [3.0 mmol/L], end with BG ≥70 mg/dL [3.9 mmol/L])	Time of the 1st BG of BGs <54 mg/dL for ≥15 consecutive minutes	Time of the last BG that ensures the BGs ≥70 mg/dL for 15 consecutive minutes	Time of the last BG <70 mg/dL – time of the 1st BG <54 mg/dL

Abbreviation: BG = blood glucose; CGM = continuous glucose monitor.

Note: Starting time and ending time are regardless of number of BG readings.

BG was captured using a CGM.

If the truncated time interval is >7 minutes but ≤15 minutes, use linear interpolation to impute the missing data at 5-minute intervals as described in Section 6.6.

If the truncated time interval is >15 minutes

- at any time, which makes the starting time undeterminable, then do not count this time interval and no episodes start.
- if it is after an episode started, which makes the ending time undeterminable, then the episode ends at the starting time of the truncation.

If an episode started and continued until the end of a CGM period, then the episode ends at the end of CGM period.

The average duration, incidence, event rate of the Level 1 or 2 and Level 2 hypoglycemia episodes will be analyzed for each CGM period as planned in Section 4.6.3.1.2. The average duration will be calculated by dividing the sum of the duration of individual episodes within 4 weeks prior to the given visit by the number of episodes and used in the analysis.

The hypoglycemia event rate (events/participant/year) will be calculated by dividing the number of episodes by the number of valid CGM days × 365.25 days.

The duration (minute) for a day= the time of last CGM value - the time of the 1st CGM value - the sum of intervals that are >15 minutes within each CGM day.

6.6.3. Mean Glucose and Glucose Management Indicator

The average glucose within a time period (a 24-hour period, daytime or nighttime) for each valid CGM day will be calculated first and then the average of daily averages of the analysis visit will be used as the mean glucose of the given analysis visit and in the analysis.

The glucose management indicator (GMI) is a new parameter estimating A1c from CGM. The GMI is based on the above mean glucose (24-hour period) by CGM using the below formula (Bergenstal et al. 2018):

$$GMI(\%) = 3.31 + 0.02392 \times \text{mean glucose (mg/dL)}$$

6.6.4. Glycemic Variability

Glycemic variability will be derived using the notation below:

i represents a time point within a time period (a 24-hour period, daytime or nighttime)

n represents the number of time points within the time period

k represents a valid CGM day within a visit

m represents the number of valid CGM days in the specific time period at a visit

$BG_{k,i}$ represents the glucose value at time point *i* on day *k* unless otherwise specified.

Sections 6.6.4.1 and 6.6.4.2 provide the derivation method for variables assessing within-day and between-day glucose variability based on CGM readings.

6.6.4.1. Within-Day Variability

For variables assessing within-day variability, first determine the variability within each valid CGM day, then average across days within 4 weeks prior to the given visit.

Within-day glucose SD (Rodbard 2009):

$$SD = \frac{1}{m} \sum_{k=1}^m SD_k = \frac{1}{m} \sum_{k=1}^m \sqrt{\frac{\sum_{i=1}^n (BG_{k,i} - \left\{ \frac{\sum_{i=1}^n BG_{k,i}}{n} \right\})^2}{n-1}}$$

Within-day glucose coefficient of variation (CV) (Clarke and Kovatchev 2009):

$$CV = \frac{1}{m} \sum_{k=1}^m CV_k = \frac{1}{m} \sum_{k=1}^m \frac{SD_k}{\left(\frac{\sum_{i=1}^n BG_{k,i}}{n} \right)} \times 100$$

The low blood glucose index (LBGI), high blood glucose index (HBGI), and blood glucose risk index (BGRI) will be calculated using the following standard formulas (Kovatchev et al. 2006).

The LBGI, HBGI, and BGRI will be derived for each valid CGM day of a visit and then averaged across days within 4 weeks prior to the given visit. The calculations of LBGI, HBGI, and BGRI take the following steps:

1. For each blood glucose (BG [mg/dL]) at the i^{th} time point, compute the following:

$$f(BG_i) = 1.509 \times [(\ln(BG_i))^{1.084} - 5.381]$$

2. Compute BG risk for each reading

$$\begin{aligned} rl(BG_i) &= 10 \times f(BG_i), \text{ if } f(BG_i) < 0; \text{ otherwise } rl(BG_i) = 0 \\ rh(BG_i) &= 10 \times f(BG_i), \text{ if } f(BG_i) > 0; \text{ otherwise } rh(BG_i) = 0 \end{aligned}$$

3. Compute LBGI and HBGI

$$LBGI = \frac{1}{n} \sum_{i=1}^n rl(BG_i)$$

$$HBGI = \frac{1}{n} \sum_{i=1}^n rh(BG_i)$$

4. Compute BGRI

$$BGRI = LBGI + HBGI$$

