For continuous measures, summary statistics will include sample size, mean, standard deviation (SD), median, minimum, and maximum for both the actual and the change from baseline measurements. For certain variables that are considered to be log-normally distributed, the geometric mean and coefficient of variation (CV) will be provided instead. Either a mixed model for repeated measures (MMRM) model or an analysis of covariance (ANCOVA) model will be used to analyze continuous outcomes. Least-squares (LS) means and standard errors (SEs) derived from the analysis models will also be displayed. Treatment comparisons will be displayed showing the treatment difference LS means and the 95% CIs for the treatment differences, along with the p-values for the treatment comparisons. For certain safety laboratory measures, log-transformed values will be analyzed in the statistical model instead. The actual, change from baseline and percentage change from baseline will be presented using the derivation based on the output from the statistical model and the assumption of log-normality.

For categorical measures, summary statistics will include sample size, frequency, and percentages. Fisher's exact test or logistic regression will be used for treatment comparisons, unless otherwise stated. For laboratory values, both conventional (CN) and System International (SI) units will be presented. Therefore, both % and mmol/mol will be presented for HbA1c, and both mg/dL and mmol/L will be presented for glucose measurements.

In this study, negative binomial regression will be used to analyze the number of hypoglycemic episodes. Group mean, instead of LS mean, will be estimated, and the delta method will be used to estimate the SE of the group mean (Qu and Luo 2015). Group mean is defined as the mean response in the treatment group for the studied population. The difference between LS mean and group mean is that the LS mean estimates the response by taking the inverse link function on mean covariates, while the group mean takes the inverse link function on individual patient covariates first and then averages over all patients. For severe hypoglycemia, the empirical

method, based on exposure-adjusted rate (calculated by the total number of events divided by total exposure), may be used for treatment comparison if the number of episodes is too small and leads to convergency issues in the negative binomial regression model.

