4.4.2. Supportive Secondary Endpoints

4.4.2.1. Other Efficacy Endpoints

The analysis of change from baseline for HbA1c at Week 52, fasting glucose by self-monitored blood glucose (SMBG) at Weeks 26 and 52, CGM (except for variability) parameters at Weeks 26 and 52 will be performed for both treatment regimen estimand and efficacy estimand.

For treatment regimen estimand, only participants with an observation at baseline or at the endpoint visit will be included in the analysis. The missing baseline will be imputed using multiple imputation under assumption of missing at random. Missing data at the endpoint visit will be imputed using either retrieved dropout or return-to-baseline multiple imputation approach determined by the criterion described for the primary efficacy endpoint in Section 4.3.2. ANCOVA analysis will be conducted similar to that for the primary endpoint. An additional term of baseline HbA1c stratum ($<8.0\%$, $\geq8.0\%$) will be added into the model for the endpoints other than HbA1c.

For efficacy estimand, participants with baseline and at least 1 post baseline observation will be included in the analysis. The longitudinal observations of actual and change from baseline in HbA1c up to Week 52 will be analyzed using the same MMRM model as for the efficacy estimand described in Section 4.3.2. The analyses of other continuous efficacy measures (insulin dose, fasting glucose, and CGM parameters) will use an MMRM model similar to that for the primary endpoint with an additional term of baseline HbA1c stratum ($<8.0\%$, $\geq8.0\%$). The variance-covariance structure in the MMRM models for fasting glucose from SMBG and insulin dose will be based on compound symmetry.

Additional analyses are as specified below.

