Event rate of Level 2 hypoglycemia events (events/participant/year) • all documented	Baseline, Weeks 0-6, 0-12, 0-26, 0-52, 12-26, 26-52, and the posttreatment period	Negative binomial regression with treatment, baseline HbA1c, and baseline Level 2 hypoglycemia rate as covariates and log (exposure/365.25 days) as the offset in the model
Event rate of Level 3 hypoglycemia events (events/participant/100 years) • all documented	Baseline, Weeks 0-26, 0-52, 26-52, and the posttreatment period	Negative binomial regression with treatment and baseline HbA1c, and baseline Level 3 hypoglycemia rate as covariates and log (exposure/36525 days) as the offset in the model If the number of events is too small to run the negative binomial regression, the exposure-adjusted rate (calculated by total number of events divided by total exposure for individual participants) will be provided, and the empirical method (see Appendix 10 [Section 6.10] for details) will be used for treatment comparison.
Event rate of Level 2/3 hypoglycemia events (events/participant/year) • all documented • nocturnal, and • non-nocturnal	Baseline, Weeks 0-6, 0-12, 0-26, 0-52, 12-26, 26-52, and the posttreatment period	A negative binomial regression with treatment, baseline HbA1c, and baseline hypoglycemia rate of the same hypoglycemia type as covariates and log (exposure/365.25 days) as the offset in the model. The plots of the mean cumulative functions (MCFs) by each treatment arm will also be created. The population mean for cumulative number of events up to time t, M(t), will be estimated using a nonparametric estimation method described by Nelson ^b .
Incidence of Level 1 hypoglycemia events • all documented	Baseline, Weeks 0-6, 0-12, 0-26, 0-52, 12-26, 26-52, and the posttreatment period	Logistic regression with treatment, baseline HbA1c, and baseline Level 1 hypoglycemia incidence as covariates
Incidence of Level 2 hypoglycemia events • all documented	Baseline, Weeks 0-6, 0-12, 0-26, 0-52, 12-26, 26-52, and the posttreatment period	Logistic regression with treatment, baseline HbA1c, and baseline Level 2 hypoglycemia incidence as covariates
Incidence of Level 3 hypoglycemia events • all documented	Baseline, Weeks 0-26, 0-52, 26-52, and the posttreatment period	Logistic regression with treatment and baseline HbA1c as covariates

Endpoint	Analysis Period ^a	Statistical Method

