$$\left[\hat{\lambda} \exp\left(-z_{1-\frac{\alpha}{2}} \sqrt{\widehat{Var}(\log(\hat{\lambda}))}\right), \hat{\lambda} \exp\left(z_{1-\frac{\alpha}{2}} \sqrt{\widehat{Var}(\log(\hat{\lambda}))}\right) \right] \quad (1)$$

The p-value for testing the null hypothesis of $H_0: \lambda = 1$ is calculated as

$$p = 2\Phi\left(\left|\log(\hat{\lambda})\right|/\sqrt{\widehat{Var}(\log(\hat{\lambda}))}\right) \quad (2)$$

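### As printed, two SAP formulas give wrong output: BGRI falls as hypoglycemia rises when high readings are held fixed, and the fallback p-value for the Level 3 rate is never below 1.

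*SAP*

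**What the plan says.** **Glucose risk indices.** SAP Section 6.6.4.1 states that LBGI, HBGI and BGRI "will be calculated using the following standard formulas" and cites a publication. Each reading is first transformed to f(BG) = 1.509 × [(ln BG)^1.084 − 5.381]. The next step, headed "Compute BG risk for each reading", gives the low-side term as "rl(BG_i) &= 10 \times f(BG_i), \text{ if } f(BG_i) < 0" and zero otherwise. The high-side term rh is 10 × f when f > 0 and zero otherwise. LBGI and HBGI are the means of rl and rh over the readings, and "BGRI = LBGI + HBGI".

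**Fallback p-value.** Section 4.1 says that for severe hypoglycemia an empirical method "may be used for treatment comparison if the number of episodes is too small" and the negative binomial model has convergence problems. The analysis table in Section 4.6.3.1.1 repeats this for the Level 3 rate: "the empirical method (see Appendix 10 [Section 6.10] for details) will be used for treatment comparison". The method itself is in Appendix 11 (Section 6.11). There, equation (1) gives a confidence interval for the rate ratio using the z quantile at 1 − alpha/2. Equation (2) gives the p-value for a ratio of 1. It begins "p = 2\Phi\left(\left|\log(\hat{\lambda" and divides the absolute log ratio by its standard error inside Phi. Phi is not defined.

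Neither formula is corrected elsewhere in the protocol or SAP.

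**The concern.** A risk score for low glucose should grow as glucose falls. The printed one goes the other way and is then added to a positive high-glucose score, so lows offset highs. An arm with more CGM hypoglycemia and the same high readings would be assigned a lower overall risk index. BGRI alone cannot show how much of its value is cancellation.

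A two-sided p-value should shrink as the estimate moves away from the null and cannot exceed 1. The printed one starts at 1 and rises. It would contradict the confidence interval beside it, for severe hypoglycemia, which Section 4.6.2.1.1 lists as a safety topic of special interest.

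**Working it through.** The plan gives no numerical result for either formula, so there is no figure to reproduce. The printed expressions were evaluated directly.

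**(a) Risk indices, inputs from Section 6.6.4.1**

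1. Zero point: f = 0 when ln BG = 5.381^(1/1.084), which gives BG = 112.52 mg/dL. Below it f is negative.
2. Example at 50 mg/dL: ln 50 = 3.912; 3.912^1.084 = 4.387; f = 1.509 × (4.387 − 5.381) = −1.500; rl = −15.0.
3. Other values of 10 × f:

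| BG (mg/dL) | 50 | 54 | 70 | 150 | 180 | 250 |
|---|---|---|---|---|---|---|
| 10 × f | −15.00 | −13.59 | −8.81 | 5.37 | 8.79 | 14.98 |

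4. rl takes the negative values of 10 × f and rh the positive ones, so BGRI = mean(rl) + mean(rh) = 10 × mean(f).
5. Illustration with high readings fixed: 50% of readings at 150 mg/dL, a share s at 50 mg/dL, the rest at the zero point, where they contribute nothing.

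| s at 50 mg/dL | HBGI | LBGI | BGRI |
|---|---|---|---|
| 1% | 0.50 × 5.372 = 2.69 | 0.01 × (−15.00) = −0.15 | 2.54 |
| 10% | 2.69 | 0.10 × (−15.00) = −1.50 | 1.19 |

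The whole fall of 1.35 comes from LBGI. Any rl that is positive at 50 mg/dL would make BGRI rise here.

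6. Cancellation: a reading at 70 (−8.81) offsets one at 180 (+8.79), the two limits of the trial's target range. A day split evenly between 50 and 250 mg/dL has BGRI = 0.5 × (−15.00) + 0.5 × 14.98 = −0.01, about the same as a flat 112.5 mg/dL.

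**(b) Fallback p-value, inputs from Section 6.11**

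Let z be the absolute log rate ratio divided by its standard error, so z ≥ 0. Phi is assumed to be the standard normal CDF. That fits the normal approximation for the log ratio and the z quantile in equation (1). Phi(z) then lies in [0.5, 1), so 2 × Phi(z) lies in [1, 2).

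| z | Printed 2 × Phi(z) | 2 × [1 − Phi(z)] |
|---|---|---|
| 0 | 1.000 | 1.000 |
| 1 | 1.683 | 0.317 |
| 1.96 | 1.950 | 0.050 |
| 3 | 1.997 | 0.003 |

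Hypothetical example showing the clash with equation (1): 20 control and 40 experimental events, 335 participants per arm (670/2) with equal exposure, and SDs of the individual counts of 0.30 and 0.45.

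- Variance of the log ratio = 335 × 0.09/400 + 335 × 0.2025/1600 = 0.0754 + 0.0424 = 0.1178; SE = 0.343.
- Rate ratio 2.0; 95% CI = 2.0 × exp(±1.96 × 0.343) = 1.02 to 3.92, which excludes 1.
- z = 0.693/0.343 = 2.02; printed p = 1.957; with the complement, p = 0.043.

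**The case against.** **The text was machine-read from PDF.** Each defect amounts to one or two missing characters: a sign, bars or an exponent in one formula, and a minus or a complement in the other. Small characters also appear to be missing elsewhere in the SAP, for example an opening bracket in the valid-daytime row of the Appendix 6 table. This cannot be ruled out. Against it, the exponent 1.084 in the same block and the minus sign in equation (1) survived. The point is therefore about the formulas as printed, and the first step is to look at the original.

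**A competent programmer would not follow either line.** A p-value above 1 would probably be caught at the first run, and the indices are tied to a cited source. That lowers the likely harm, and nothing in the documents shows that the analysis program follows the printed lines. But the SAP is the specification, and a silent departure from it is undocumented. A low BGRI, unlike an impossible p-value, might not be noticed.

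**The glucose days are constructed.** True. They establish direction, not a likely effect size in this trial.

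**Stronger readings that the documents do not support:**

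- *LBGI is sound apart from its sign.* This holds only if the source uses the absolute value of f. If it uses another non-negative form, such as a square, LBGI would also change in scale and weighting, and so might HBGI. The documents do not show which form applies.
- *rh is wrong too.* As printed it is already non-negative. All that can be said is that it should be checked against the same source.
- *The trial's hypoglycemia conclusions are at risk.* Time below 54 and 70 mg/dL and the CGM-derived episodes do not use these indices, and the participant-reported rates use neither formula unless the Level 3 fallback is triggered.

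**Conclusion.** Both formulas are wrong as printed and should be corrected. Part (a) follows from the printed algebra and the SAP's own description of the quantity as a risk. Part (b) also rests on reading Phi as the lower-tail normal CDF, which the SAP does not state but which its equation (1) supports.

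The reach is limited. LBGI and BGRI are derived under glycemic variability, an other secondary endpoint without multiplicity adjustment. Section 4.4.2.1 leaves variability out where it says that analysis of "CGM (except for variability) parameters at Weeks 26 and 52 will be performed for both treatment regimen estimand and efficacy estimand". Within-day and between-day SD and CV, the mean of daily differences, and times in range are untouched. Part (b) affects only the p-value of a conditional comparison for a tertiary safety endpoint, and the interval in equation (1) remains correct in form. The primary and key secondary tests are unaffected.

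**What to change.** First compare both formulas with the original PDF and with the analysis program, in case a character was lost in conversion.

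- Section 6.6.4.1: print rl in the non-negative form used by the source the SAP cites, and confirm that rh has the same form. Whether the scale or weighting of LBGI and HBGI then changes is settled by that source.
- Section 6.11, equation (2): print p = 2 × [1 − Phi(z)], with z the absolute log rate ratio over its standard error, and define Phi as the standard normal CDF.
- Editorial: the Level 3 rate row in Section 4.6.3.1.1 should point to Appendix 11 (Section 6.11). Section 4.6.2.1.2 should point to Appendix 9 (Section 6.9) for persistent-recurrent hypoglycemia, as the text of Section 4.6.3.1.1 already does. Both now point to Appendix 10, which is the laboratory abnormality table.

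The cost is a few characters in two formulas, one definition, two cross-references and a program check. No new data are needed and no endpoint changes.

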6.6.4.2. Between-Day Variability

For variables assessing between-day variability, first determine the variability for each time point across days 4 weeks prior to the given visit then average across all time points.

Between-day glucose SD (Rodbard 2009):

$$SD = \frac{1}{n} \sum_{i=1}^n SD_i = \frac{1}{n} \sum_{i=1}^n \sqrt{\frac{\sum_{k=1}^m (BG_{k,i} - \left\{ \frac{\sum_{k=1}^m BG_{k,i}}{m} \right\})^2}{m-1}}$$

Between-day glucose CV (Kovatchev et al. 2009):

$$CV = \frac{1}{n} \sum_{i=1}^n CV_i = \frac{1}{n} \sum_{i=1}^n \left(\frac{SD_i}{\left\{ \frac{\sum_{k=1}^m BG_{k,i}}{m} \right\}} \right) \times 100$$

Mean of daily differences (MODD): this parameter is calculated as the mean of absolute differences between glucose values at corresponding time points of consecutive days.

$$\text{MODD} = \frac{1}{m-1} \sum_{k=1}^{m-1} \frac{\sum_{i=1}^n |\text{BG}_{k+1,i} - \text{BG}_{k,i}|}{n}$$

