6.6. Appendix 6: Derivation of CGM Variables

For all study participants meeting study entry criteria, a CGM device will be inserted and activated at (Visit 2). Participants will be unblinded to the CGM system and wear the study-provided CGM during the study duration.

For the primary analysis, the CGM data will be included in the analysis only if at least 70% of the total measures in the analysis period are obtained (defined as a valid CGM period). For example, the 24-hour period will have 288 measures and the minimum number of measures will be 202. All the CGM derivations are based on the data from valid CGM period unless otherwise specified. A sensitivity analysis will be done for selected parameters by including CGM days with at least 10% of data and at least 3 such CGM days within the given CGM period.

The CGM variables will be derived for each CGM day when the analysis data meet the above requirement. The CGM variables for an analysis visit/period will be derived for participants with at least 3 valid CGM days during the corresponding analysis visit/period. For the analysis visits, the CGM readings from approximately 2 weeks prior to Week 0 (Visit 3), 4 weeks prior to Weeks 4, 8, 12, 16, 26, 36, 40, 44, 48, and 52 (Visit 7, 11, 15, 17, 22, 25, 26, 27, 28, and 29), 6 weeks prior to Weeks 22 and 32 (Visit 20 and 24) and 4 weeks prior to the end of safety follow-up (Visit 802) will be used. To understand the overall control in different periods (for example, the titration period), the CGM variables may also be derived for the following analysis periods: 0 through 12, 12 through 26, 26 through 52, 0 through 26, and 0 through 52 weeks of treatment period.

Linear interpolation will be used to impute the missing glucose readings during intervals >7 minutes and ≤ 15 minutes. Missing data will be imputed at a 5-minute interval using the BG value before and the one after the interval.

For example, the BG reading before the interval is 50 mg/dL at time 100 min, and the BG reading after interval is 70 at time 115 min, then the missing records will be imputed as:

- at time 105 min, BG reading= $50+5\times(70-50)/(115-100)=56.7$,
- at time 110 min, BG reading= $50+10\times(70-50)/(115-100)=63.3$

Glucose reading intervals >15 minutes will be treated as missing data and not be counted in the length of the analysis periods.

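### The MODD formula in SAP 6.6.4.2 pairs successive valid CGM days rather than consecutive calendar days, so it departs from its own definition when wear has gaps; the expected effect is small

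*SAP*

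**What the plan says.** SAP 6.6.4.2 describes MODD in words as the average absolute difference between "glucose values at corresponding time points of consecutive days". The formula below takes, at each time point, the absolute difference between day k+1 and day k. It averages these over the n time points, sums over k = 1 to m-1 and divides by m-1.

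The notation is set in SAP 6.6.4: k "represents a valid CGM day within a visit", and m "represents the number of valid CGM days in the specific time period at a visit".

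SAP 6.6 sets the data requirements. For a full day, "the 24-hour period will have 288 measures and the minimum number of measures will be 202". CGM variables are derived for "participants with at least 3 valid CGM days during the corresponding analysis visit/period". The between-day measures use the 4 weeks before the visit.

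Glucose variability by CGM at Weeks 26 and 52 is listed among the other secondary endpoints (SAP 1.1). SAP 2.1 applies no multiplicity adjustment to that tier. SAP 4.4.2.1 leaves variability out of the treatment-regimen analyses, so it is analysed under the efficacy estimand only.

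**The concern.** The verbal definition and the formula agree only when no invalid day falls between two valid ones. Where one does, k+1 is the next valid day, whatever the calendar gap, and the difference is no longer a daily one. SAP 6.6 has no rule that valid days be adjacent, no rule that drops pairs spanning a gap, and no statement that consecutive means consecutive among valid days.

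Two things are at stake. First, if glucose on nearby days is more alike than on distant days, a pair spanning a gap tends to give a larger difference, so MODD partly reflects sensor wear. Second, a programmer who follows the sentence and one who follows the formula would obtain different values for the same participant.

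A smaller gap sits beside this. The formula divides by a fixed n, but two valid days need not have readings at the same times, and the SAP does not say how unmatched time points are handled.

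**Working it through.** The documents state no MODD value, so there is no figure of the plan to reproduce. The one related threshold checks: 0.70 × 288 = 201.6, rounded up to 202.

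**Formula against definition.** Illustration with an assumed steady drift of 2 mg/dL per day in a 28-day window:

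| Valid days | Printed formula | Calendar-adjacent pairs only |
|---|---|---|
| All 28 | 2.0 | 2.0 (27 pairs) |
| 1, 10, 28 | (18 + 36)/2 = 27.0 | undefined (no pair) |
| 1-3 and 13-15 | (2 + 2 + 20 + 2 + 2)/5 = 5.6 | 2.0 (4 pairs) |

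The second row meets the three-day minimum. The drift is chosen to expose the mechanism and is not a forecast.

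**Average size, closed form.** For normally distributed readings the expected absolute difference between two days is proportional to √(1 − ρ), where ρ is the time-matched correlation. Assume ρ = 0.15 to 0.30 for adjacent days and 0.05 for any non-adjacent pair. A non-adjacent pair is then larger by:

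- √(0.95/0.85) = 1.057, or about 6%
- √(0.95/0.70) = 1.165, or about 16.5%

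If a share v of days is valid at random, a share 1 − v of the pairs is non-adjacent:

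- v = 0.90: 0.10 × 6% to 16.5% = 0.6% to 1.7%
- v = 0.80: 0.20 × 5.7% to 16.5% = 1.1% to 3.3%

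A participant with no adjacent valid days would carry the full 6% to 16.5%.

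**Average size, simulation.** Assumed inputs: 28 days, autoregressive day levels with SD 30 mg/dL, independent reading SD 30 mg/dL, days invalid at random, 400 participants per row. Shift of the printed formula relative to calendar-adjacent pairs:

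| Day-level correlation | 5% invalid | 20% invalid | 50% invalid |
|---|---|---|---|
| 0 | 0.2% | 0.0% | 0.2% |
| 0.3 | 0.2% | 1.4% | 3.2% |
| 0.6 | 0.5% | 1.4% | 5.7% |
| 0.9 | 0.2% | 0.8% | 3.4% |

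The true shift in the first row is nil, so it gives a rough idea of the simulation noise. The share of non-adjacent pairs came out at about the share of invalid days, as the closed form assumes. With equal variances the time-matched adjacent correlation is half the day-level value, so 0.6 corresponds to 0.30. The simulated 1.4% is below the closed-form 3.3% because the correlation two days apart is 0.36/2 = 0.18, not 0.05.

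**Block gaps.** One interior 6-day gap in 28 days leaves 22 valid days (79%) and 21 pairs, of which 1 is non-adjacent (4.8%). The closed-form shift is 4.8% × 5.7% to 16.5% = 0.3% to 0.8%, well below the result for random gaps at similar validity.

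**Between arms.** On the same assumptions, a 5-point difference in day validity between arms would shift the comparison by 0.05 × 5.7% to 16.5% = 0.3% to 0.8% of MODD.

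**Matched time points.** Two valid days may have as few as 202 + 202 − 288 = 116 of 288 time points in common.

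**The case against.** The best reply is that consecutive days here means consecutive valid days. SAP 6.6.4 defines k as a valid day just before the formulas, and SAP 6.6 bases CGM derivations on valid periods. On that reading the formula is what was intended and only the word valid is missing. The reading is possible, and the formula itself leaves no doubt about which days are paired. But the SAP does not state it, and the parameter is named for daily differences. For a participant with gaps, the printed formula gives something else.

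A reader might go further and infer that an arm with poorer wear will look more variable. The documents do not support that. Both arms have the same device, visit schedule and compliance rules (Protocol 1.3 and 8.1.1.2), nothing shows differential wear, and similar gaps in both arms would largely cancel from the comparison.

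Other parts of the reply also stand. The assumption that differences grow with the gap has no source in the documents. Sensors last up to 10 days and capture below 80% prompts re-education (Protocol 8.1.1.2), so block gaps are plausible and a participant with no adjacent valid days would be unusual. SAP 4.4.2.1.1 already plans summaries of missing CGM data by day, week and period. Within-day and between-day SD and CV do not depend on adjacency.

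**Conclusion.** The mismatch is real and can be read directly from the SAP: the definition uses consecutive days, the formula uses successive valid days, and the three-day minimum lets a value arise with no consecutive-day pair.

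The consequence is small. Under the assumed inputs the average within-participant shift is about 0% without day-to-day correlation and roughly 1-3% at 20% randomly invalid days with positive correlation. It is lower when gaps come in blocks. Only participants with sparse valid days could be shifted more. All of these figures rest on assumed correlations and gap patterns.

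The documents do not establish bias in the treatment comparison, because that would need differential wear. The primary and key secondary analyses are untouched. One of several variability measures, under an endpoint without multiplicity adjustment, is affected. This is a worthwhile correction to the derivation, not a threat to the trial's conclusions.

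**What to change.** In SAP 6.6.4.2, restrict the MODD sum to pairs of valid CGM days that are one calendar day apart. Within each pair, use only time points present on both days and divide by the number of such points. Average over the number of qualifying pairs, and set MODD to missing if there is none. Apply the same rule to the 24-hour, daytime and nighttime versions.

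The cost is one line in the SAP and one date check in the program. SAP 4.1 allows a change of this kind to be described in the SAP or the clinical study report. The downside is that MODD becomes missing for a few participants with poor wear, so missingness depends on wear. Report how many are affected, by arm and visit.

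If pairing successive valid days was in fact intended, the SAP should say so. That removes the ambiguity and keeps every pair, but MODD would then mix lags and would not be a mean of daily differences for participants with gaps.
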